3.0 Protocol Synopsis

Protocol Number	CL00003
Protocol Title	Evaluation of EndoZip™ System (AS) in Obese Patients who failed to reduce weight with non-surgical weight-loss methods
Study Sponsor	
NiTINotes, [name]
 
[contact]
 
[contact]

Sponsor Representative	
[name] VP QA, Regulatory and Medical Affairs

Study Type	Pilot study
Study Product	EndoZip™ System (AS)
Study Location	Europe, Israel
Study Centers	
 1. Hospital Universitario HM Sanchinarro, Madrid, SPAIN 2. Fondazione Policlinico Universitario Agostino Gemelli IRCCS (CERTT), Rome, Italy 3. Rabin Medical Center, Petah Tikva, Israel

	
Title: Evaluation of EndoZip™ System (AS) in Obese Patients who failed to reduce weight with non-surgical weight-loss methods
	
Document No: CL00003	Rev: 1.0	Page: 9 of 83

Investigators	
 1. [name] 2. [name] 3. [name]
Study Duration	The duration for each participant will be 12 months; the total study duration is expected to be approx. 18 months
Study Design	The study is planned as a multicenter, prospective, single-arm, open-label, controlled clinical trial.
Planned Visits	
 • Office visits: 1 week, and 1, 2, 4, 6, 8, 10, and 12 month(s) • Remote follow up (by Phone): 3, 5, 7, 9, and 11 month(s) • Endoscopy follow up: 2 and 6 months • Motility evaluation by Gastric Emptying Breath Test (GEBT): 6 months • Physical examination, vital signs, waist circumference and BMI: 1 week, 1, 2, 4, 6, 8, 10 and 12 months • Blood tests: 2, 6 and 12 months • IWQOL-Lite: 2, 6 and 12 months • Sleep Apnea (only for the relevant population): 2, 6 and 12 months
Patient Population	Male and Female with obesity, BMI of 30-40 kg/m ² , between the ages of 21 and 70 who failed to reduce weight with non-surgical weight-loss methods
Planned # of Patients	Up to 45 patients
Planned # of Sites	Up to 5 clinical sites
Planned # of Patients per Site	Up to 20

	Title: Evaluation of EndoZip™ System (AS) in Obese Patients who failed to reduce weight with non-surgical weight-loss methods	
Document No: CL00003	Rev: 1.0	Page: 10 of 83

Study Objective	
The objective of this study is to evaluate the safety and effectiveness of the EndoZip system procedure, coupled with lifestyle modifications, for weight reduction in obese patients with BMI of 30-40 kg/m².

Study Procedures	
Visit 1: Baseline Screening Visit
 
 After signing informed consent, patients will be screened for study eligibility by: Eligibility Criteria Demographics, Medical history, Obesity History Physical examination Vital signs (blood pressure and heart rate - supine, pulse, body temperature, respiratory rate (RR) and SpO₂) Body Weight, Height and Waist circumference Laboratory evaluations (Hematology, CBC with differential, PTT, PT and INR, Comprehensive Metabolic Panel (Kidney and liver functions – blood glucose, HbA1c, Urinalysis, TSH, fasting lipid panel) Motility evaluation by Gastric Emptying Breath Test (GEBT) Influence of Weight on Quality of Life (IWQOL) questionnaire Psychological health questionnaire-9 (PHQ-9) Patients with diagnosed Sleep Apnea will be tested using WatchPAT 200 
Visit 2: Procedure Day
 
 Physical examination Vital signs (blood pressure and heart rate - supine, pulse, body temperature, respiratory rate (RR) and SpO₂) Body Weight, Height and Waist circumference Pregnancy test Electrocardiogram (ECG) evaluation Endoscopy screening procedure

	Title: Evaluation of EndoZip™ System (AS) in Obese Patients who failed to reduce weight with non-surgical weight-loss methods	
Document No: CL00003	Rev: 1.0	Page: 11 of 83

	
 • EndoZip Procedure • EndoZip's Usability Questionnaire • Meeting with dietitians/nutritionists • AE / SAE 
Phone call follow up
 
At day 1 after patient's discharge to verify the patient's well-being.
 
Visit 3: Follow up 1 week after patient's discharge day:
 
 • Physical examination • Vital signs (blood pressure and heart rate - supine, pulse, body temperature, respiratory rate (RR) and SpO2) • Body Weight, Height and Waist circumference • Meeting with dietitians/nutritionists - lifestyle modifications counseling • Concomitant medication • AE / SAE 
Visit 4: Follow up 1 month after procedure day
 
 • Physical examination • Vital signs (blood pressure and heart rate - supine, pulse, body temperature, respiratory rate (RR) and SpO2) • Body Weight, Height and Waist circumference • Meeting with dietitians/nutritionists - lifestyle modifications counseling • Concomitant medication • AE / SAE 
Visit 5: Follow up 2 months after procedure day:
 
 • Physical examination • Vital signs (blood pressure and heart rate - supine, pulse, body temperature, respiratory rate (RR) and SpO2) • Body Weight, Height and Waist circumference • Meeting with dietitians/nutritionists - lifestyle modifications counseling

	
Title: Evaluation of EndoZip™ System (AS) in Obese Patients who failed to reduce weight with non-surgical weight-loss methods
	
Document No: CL00003	Rev: 1.0	Page: 12 of 83

	
 • Laboratory evaluations (Hematology, CBC with differential, Comprehensive Metabolic Panel (Kidney and liver functions – blood glucose, HbA1c, Urinalysis, fasting lipid panel) • Endoscopy follow up procedure • IWQOL questionnaire • Concomitant medication • AE / SAE • Patients with diagnosed Sleep Apnea will be tested using WatchPAT 200
	
Visit 6: Follow up 6 months after procedure day:
 
 • Physical examination • Vital signs (blood pressure and heart rate - supine, pulse, body temperature, respiratory rate (RR) and SpO2) • Body Weight, Height and Waist circumference • Meeting with dietitians/nutritionists - lifestyle modifications counseling • Laboratory evaluations (Hematology, CBC with differential, Comprehensive Metabolic Panel (Kidney and liver functions – blood glucose, HbA1c, Urinalysis, TSH, fasting lipid panel) • Motility evaluation by Gastric Emptying Breath Test (GEBT) • Endoscopy procedure • IWQOL questionnaire • Concomitant medication • AE / SAE • Patients with diagnosed Sleep Apnea will be tested using WatchPAT 200
	
Visit 7: Follow up 12 months after procedure day:
 
 • Physical examination • Vital signs (blood pressure and heart rate - supine, pulse, body temperature, respiratory rate (RR) and SpO2) • Body Weight, Height and Waist circumference • Meeting with dietitians/nutritionists - lifestyle modifications counseling • Laboratory evaluations (Hematology, CBC with differential, Comprehensive Metabolic Panel (Kidney and liver functions – blood glucose, HbA1c, Urinalysis, fasting lipid panel)

	
Title: Evaluation of EndoZip™ System (AS) in Obese Patients who failed to reduce weight with non-surgical weight-loss methods
	
Document No: CL00003	Rev: 1.0	Page: 13 of 83

	
 • IWQOL questionnaire • Concomitant medication • AE / SAE • Patients with diagnosed Sleep Apnea will be tested using WatchPAT 200
	
Additional follow up visits: Patients will receive brief (30min) telephone calls in the months that do not include in person visits (in months 3, 5, 7, 9, and 11 after the procedure). These counseling sessions are primarily designed to improve adherence to recommendations to consume a healthy diet and increase physical activity to promote weight loss and overall health.
 
Additional in person visits In addition to the visits above, patients will visit the clinic in 4, 8, and 10 months after the procedures. In these visits, patient will meet the physicians and the dietitians/nutritionists. These counseling sessions are primarily designed to improve adherence to recommendations to consume a healthy diet and increase physical activity to promote weight loss and overall health.

Primary Endpoint	
The effectiveness of the EndoZip system will be assessed by the following co-primary endpoints:
 
 1. Mean percent of total body weight loss (%TBWL) after 12 months. 2. Percentage of patients with a reduction in %TBWL of at least 5% at 12 months.
Secondary Endpoints	
The following secondary endpoints will be evaluated:
 
 1. Percent of excessive weight loss (%EWL) over 6 and 12 months. 2. Reduction of weight and waist circumference over 6 and 12 months. 3. Impact of EndoZip procedure on gastric motility at 6 months. 4. Changes in Weight-related Quality of Life (IWQOL) Questionnaire scores at 6 and 12 months 5. Time analysis including procedure duration, anesthesia duration, patient recovery duration

	
Title: Evaluation of EndoZip™ System (AS) in Obese Patients who failed to reduce weight with non-surgical weight-loss methods
	
Document No: CL00003	Rev: 1.0	Page: 14 of 83

	
6. Change in comorbid conditions over 12 months evaluated by:
 
 Blood pressure Glucose, HbA1c Lipid levels (Total Cholesterol, LDL-C, HDL-C, and triglycerides) Sleep Apnea 
7. Usability evaluation and physician's satisfaction based on a questionnaire

Safety Endpoints	
The following safety variables will be recorded at regular intervals during the study:
 
 Physical examination Vital signs (blood pressure and heart rate - supine, pulse, body temperature, respiratory rate (RR) and SpO2) Telemetry monitoring (continuous ECG, respiratory rate, SpO2 monitoring) during procedure and at recovery Clinical laboratory tests (hematology, clinical chemistry, lipid profile and urinalysis) Adverse event (AE) assessments Monitoring of sleep apnea (If relevant) 
Safety will be characterized through a summary of the incidence of adverse events and serious adverse events by relation to study treatment. A Data Safety Monitoring Board (DSMB) will review and adjudicate all serious device related and non-related adverse events and any other events deemed necessary.

Randomization	NA- single arm study
Eligibility Criteria	
Inclusion Criteria
 
 Age 21-70 BMI ≥ 30 and ≤ 40 kg/m². Willingness to comply with the substantial behavioral modifications program as required by the procedure. Patients with history of failure with non-surgical weight-loss methods. Willingness to follow protocol requirements, including signed informed consent, routine follow-up schedule, completing laboratory tests,

	Title: Evaluation of EndoZip™ System (AS) in Obese Patients who failed to reduce weight with non-surgical weight-loss methods	
Document No: CL00003	Rev: 1.0	Page: 15 of 83

	
completing IWQOL questionnaire and completing the medically supervised diet and behavior modification program.
 
 6. Residing within a reasonable distance from the investigator's office and able to travel to the investigator to complete all routine follow- up visits. 7. Ability to give informed consent. 8. Women of childbearing potential (i.e., not post-menopausal or surgically sterilized) must agree to use adequate birth control methods. 
Exclusion Criteria
 
 1. Prior surgery of any kind on the gastrointestinal tract (except uncomplicated cholecystectomy or appendectomy). 2. Patients with history of small bowel or colonic obstruction, and/or adhesive peritonitis and/or abdominal adhesions. 3. Patients with any inflammatory disease 4. Patients with history of cancer in the gastrointestinal tract. 5. Potential upper gastrointestinal bleeding conditions such as a history of angioectasias. 6. A known gastric mass or gastric polyps > 1 cm in size. 7. Patients with TG >500 or LDL >190 8. A known hiatal hernia > 4cm of axial displacement of the z-line above the diaphragm or severe or intractable gastro-esophageal reflux symptoms while on maximal medical therapy. 9. A structural abnormality in the esophagus or pharynx such as a stricture or diverticulum that could impede passage of the endoscope. 10. Patient with motility disorders of the GI tract or intractable constipation 11. Patients with known coagulation disorder (INR >1.5) or on anticoagulation therapy. 12. Type 1 diabetes or Type 2 diabetes with a HgbA1c >8 in 6 weeks prior the procedure or use of any medication for diabetes other than metformin. Patients with any serious health condition unrelated to their weight that would increase the risk of endoscopy 13. Patients with chronic abdominal pain 14. Patients with hepatic insufficiency or cirrhosis 15. Patients that used an intragastric device for weight loss within 2 years prior to this study.
--	--

	
Title: Evaluation of EndoZip™ System (AS) in Obese Patients who failed to reduce weight with non-surgical weight-loss methods
		
Document No: CL00003	Rev: 1.0		Page: 16 of 83

	
16. Patients with psychological health questionnaire-9 (PHQ-9) score of 10 or higher.
 
17. Patients receiving daily prescribed treatment with high dose aspirin (> 100mg daily), anti-inflammatory agents, anticoagulants or other gastric irritants.
 
18. Patients with history or current abuse of drugs or alcohol
 
19. Patients who are unable or unwilling to take prescribed proton pump inhibitor medication
 
20. egg, milk, or wheat allergy (unable to go through the GEBT)
 
21. Patients who are pregnant or breast-feeding.
 
22. Patients who are taking medications that cause weight loss
 
23. Patients with Severe cardiopulmonary disease or other serious organic disease which might include known history of coronary artery disease, Myocardial infarction within the past 12 months, poorly-controlled hypertension, required use of NSAIDs
 
24. Patients taking medications on specified hourly intervals that may be affected by changes to gastric emptying, such as anti-seizure or anti-arrhythmic medications
 
25. Patients who are taking corticosteroids, immunosuppressants, and narcotics
 
26. Symptomatic congestive heart failure, cardiac arrhythmia or unstable coronary artery disease.
 
27. Pre-existing respiratory disease such as chronic obstructive pulmonary disease (severe COPD), pneumonia or cancer.
 
28. Diagnosis of autoimmune connective tissue disorder (e.g. lupus, HIV, erythematous, scleroderma) or immunocompromised.
 
29. Specific diagnosed genetic disorder such as Prader Willi syndrome (motility disorder)
 
30. Eating disorders including night eating syndrome (NES), bulimia, binge eating disorder, or compulsive overeating
 
31. Known history of endocrine disorders affecting weight such as uncontrolled hypothyroidism.

--	--

Statistical Considerations

	Title: Evaluation of EndoZip™ System (AS) in Obese Patients who failed to reduce weight with non-surgical weight-loss methods	
	Document No: CL00003	Rev: 1.0

Analysis Populations	
Full Analysis Set (FA): includes all enrolled patients, excluding the patients who enrolled in the run-in period, who underwent EndoZip procedure.
 
Modified Full Analysis Set (mFA): The modified full (mFA) analysis set will include all patients who have at least one post initiation follow up visit and met the study Eligibility Criteria.
 
Per-Protocol (PP) analysis set: includes all patients from the mFA set who do not have any major protocol violations.
 
Statistical Analysis of Analysis Sets Safety assessments will be performed on the FA analysis set.
 
The mFA will serve as the principal data analysis set for the primary and secondary statistical efficacy endpoints. The primary, secondary efficacy assessment will also be performed on the PP and FA cohorts for descriptive purposes and to show consistency of study results.

Sample Size Estimation	
This is a pilot study that will include up to 45 patients; no statistical considerations were made to determine the sample size.

Statistical Analyses	
General Methods: Statistical analyses will be mainly descriptive in nature. Any statistical tests if performed will be two-sided, unless otherwise stated. Study data will be summarized with descriptive statistics and presented in tables and figures. Continuous variables will be summarized by a mean, standard deviation, minimum, median and maximum and categorical variables by a count and percentage. If multiple measurements are taken in a single patient, statistics described below will be appropriately modified to accommodate the within patient correlation. Any deviation from specified statistical plan will be in addition to "per protocol" analysis and will be reported as such Post-hoc analysis will be conducted according to the existing data gathered, if necessary.
 
Handling of the Type I Error

	Title: Evaluation of EndoZip™ System (AS) in Obese Patients who failed to reduce weight with non-surgical weight-loss methods	
Document No: CL00003	Rev: 1.0	Page: 18 of 83

	
The overall significance level for this study is 5%, confidence intervals will be two-sided using a 95% confidence level, except for treatment by site interaction that will be tested at a significance level of 10%.
 
Primary Endpoints
 
The %TBWL at each visit will be calculated as $100 * (\text{Weight(BL)} - \text{Weight(Visit)}) / \text{Weight(BL)}$, where weight is measured in kilograms. %TBWL will be summarized with descriptive statistics at each follow-up visit.
 
%TBWL will be evaluated by using repeated measures analysis of covariance (ANCOVA MIXED model). Baseline weight, center and visit will be used as covariates. Baseline weight will be entered as a continuous variable so that the potential for collinearity problems will be minimized.
 
The unstructured covariance matrix structure will be used. If the model doesn't converge, then either the compound symmetry or autoregressive (whichever model has the lower AIC statistic) covariance matrix structure will be used instead. For this evaluation, no imputation of missing data is considered beyond the model estimates.
 
The model estimated mean %TBWL at each visit will be presented with 95% confidence interval and level of significance.
 
A count and percentage of patients achieving at least 5% TBWL will be presented with exact 95% confidence interval.
 
Subset Analysis of the primary endpoint:
 
Additionally, the %TBWL median, mean and standard deviation and percent of patients with greater than 5%TBWL will be summarized. Covariates may include demographic data (sex, age, BMI) or other baseline characteristics.
 
Secondary Endpoints
 
Excess Weight Loss % (EWL%)
 
EWL% of patients at 1, 2, 6 and 12 month(s) by study group will be summarized with descriptive statistics with 95% confidence intervals.
 
The percent excess weight loss (%EWL) will be calculated as $(\text{Weight(BL)} - \text{Weight(Visit)}) / \text{ExcessWeight(BL)}$, where ExcessWeight(BL) is calculated as difference

--	--

	
Title: Evaluation of EndoZip™ System (AS) in Obese Patients who failed to reduce weight with non-surgical weight-loss methods
	
Document No: CL00003	Rev: 1.0	Page: 19 of 83

	
between the patient's baseline weight in kilograms and the kilograms at which the patient's BMI would be 25.
 
Change of Weight and Waist Circumference Over 12 Months from Baseline Change from baseline in BMI at 1, 2, 6 and 12 month(s) by study group will be summarized with descriptive statistics with 95% confidence intervals.
 
Changes in Weight-related Quality of Life (IWQOL) Questionnaire at 12 months IWQOL questionnaire records will be summarized by study groups will be summarized with descriptive statistics with 95% confidence intervals.
 
Time analysis Time analysis including procedure duration, anesthesia duration, patient recovery duration will be evaluated and will be summarized with descriptive statistics with 95% confidence intervals

--	--

	Title: Evaluation of EndoZip™ System (AS) in Obese Patients who failed to reduce weight with non-surgical weight-loss methods	
Document No: CL00003	Rev: 1.0	Page: 20 of 83

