10.0 Study Design

[figure not shown]
This multicenter, prospective, single arm study will include up to 45 patients (10-20 patients per site), aimed at evaluating the performance of the EndoZip System in obese patients who failed to reduce weight with non-surgical weight-loss methods.

The first two (2) patients in each site will be considered as run-in period, to compensate for any learning curve that may be required for the EndoZip performance evaluation.

Patients will be enrolled at up to 5 clinical sites in Europe and Israel. Patients who meet the eligibility criteria is expected to come the clinic for at least 10 visits.

	
Title: Evaluation of EndoZip™ System (AS) in Obese Patients who failed to reduce weight with non-surgical weight-loss methods
	
Document No: CL00003	Rev: 1.0	Page: 33 of 83

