10.1 Study Flow Chart

11.0 Patient Selection and Enrollment

After being informed of the nature of the study, the patient will sign a written informed consent form (ICF) that has been approved by the appropriate Institutional Ethics Committee (IEC) and regional Competent Authority (CA). Enrollment of up to 45 patients is planned.

Patients will be considered for the study if they meet the specific inclusion/exclusion criteria. The criteria for enrollment must be followed explicitly.

	Title: Evaluation of EndoZip™ System (AS) in Obese Patients who failed to reduce weight with non-surgical weight-loss methods		
Document No: CL00003	Rev: 1.0	Page:	34 of 83

Enrollment completion is expected to take place up to 6 months following IEC approval of the study.

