13.1.2 Screen Failures

A patient is considered enrolled in the study when the ICF is signed. Only patients who receive study-assigned procedures will be followed. Patients who provide study consent, but then are determined to be ineligible will be considered screening failures and will not require additional study follow-up. The reason for the screening failure will be clearly documented, the Patient "Enrollment and Visit Log" will be completed and the patient eligibility section in visit 1 as well as a "Study Completion" form will be completed in the eCRF.

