14.0 Statistical Analysis

14.1 Sample Size Determination

This is a pilot study that will include up to 45 patients; no statistical considerations were made to determine the sample size.

The first two (2) patients per site will be considered as run-in period, to compensate for any learning curve that may be required for the EndoZip performance evaluation.

Safety evaluation will include all enrolled patients.

	Title: Evaluation of EndoZip™ System (AS) in Obese Patients who failed to reduce weight with non-surgical weight-loss methods		
Document No: CL00003	Rev: 1.0	Page:	53 of 83

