14.2 Description of statistical methods

14.2.1 Analysis of Populations

Full Analysis Set (FA): includes all enrolled patients who undergone EndoZip procedure, excluding patients who enrolled in the run-in period.

Modified Full Analysis Set (mFA): The modified full (mFA) analysis set will include all patients who have at least one post initiation follow up visit and met the study Eligibility Criteria, and enrolled after the run-in period.

Per-Protocol (PP) analysis set: includes all patients from the mFA set who do not have any major protocol violations, and enrolled after the run-in period, and enrolled after the run-in period.

Statistical Analysis of Analysis Sets: Safety assessments will be performed on all enrolled patients set.

The mFA will serve as the principal data analysis set for the primary and secondary statistical efficacy endpoints. The primary, secondary efficacy assessment will also be performed on the PP and FA cohorts for descriptive purposes and to show consistency of study results.

14.2.2 General Methods:

Statistical analyses will be mainly descriptive in nature. Any statistical tests if performed will be two-sided, unless otherwise stated.

Study data will be summarized with descriptive statistics and presented in tables and figures. Continuous variables will be summarized by a mean, standard deviation, minimum, median and maximum and categorical variables by a count and percentage. If multiple measurements are taken in a single patient, statistics described below will be appropriately modified to accommodate the within patient correlation.

Any deviation from specified statistical plan will be in addition to “per protocol” analysis and will be reported as such Post-hoc analysis will be conducted according to the existing data gathered, if necessary.

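### The safety analysis set is defined in two conflicting ways, and neither is the set of patients treated with the device

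*Combined protocol and SAP*

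**What the plan says.** The synopsis, under Analysis Populations, assigns safety to the full analysis (FA) set: "Safety assessments will be performed on the FA analysis set". It defines that set thus: "includes all enrolled patients, excluding the patients who enrolled in the run-in period, who underwent EndoZip procedure". Section 10.0 explains the exclusion: "The first two (2) patients in each site will be considered as run-in period", the purpose being to absorb a learning curve.

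The body of the protocol says otherwise. Section 14.1 states "Safety evaluation will include all enrolled patients", and section 14.2.1 states "Safety assessments will be performed on all enrolled patients set". Section 14.2.1 keeps the run-in exclusion in its own FA definition, so its safety set cannot be the FA set under another name.

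The word enrolled is defined in section 13.1.2: "A patient is considered enrolled in the study when the ICF is signed. Only patients who receive study-assigned procedures will be followed". Section 11.0 appears to use it more loosely, for patients who pass the eligibility criteria: "Enrollment of up to 45 patients is planned" and "The criteria for enrollment must be followed explicitly". Section 14.7 also counts as enrolled patients who already have two months of follow-up.

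**The concern.** Safety is part of the primary objective in section 8.1, and section 9.1 places the incidence of adverse and serious adverse events under the primary endpoints. The denominator of that result, and which patients' events count in its numerator, depend on which page the analyst follows.

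The patients dropped by the synopsis rule are not a random subset. They are set aside because operator experience may affect results, so they are the patients in whom a procedural complication is most plausible. The device is also an updated configuration, redesigned after a serious technical failure (section 6.3.1). Excluding run-in patients may be defensible for efficacy. For safety it removes relevant exposure from the reported rates.

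The body rule errs differently. If enrolled means consented, screen failures enter the denominator. They are not followed, and section 14.3 sends pre-procedure events to medical history unless they are serious and caused by a protocol-mandated procedure. They can therefore add almost nothing to the numerator.

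If the choice is still open when the events are known, it can be made in the light of the results.

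**Working it through.** The plan has no calculation to reproduce, because section 14.1 says N has no statistical basis. The check measures how far the rules differ.

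**Inputs from the documents.** Up to 45 patients (section 14.1); two run-in patients per site (sections 10.0 and 14.1); three named sites and at most five (synopsis); two-sided 95% intervals (section 14.2.3).

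**Assumptions.** Forty-five patients are treated, and every run-in patient is treated. The event counts are illustrations. The documents give no screen-failure rate, so a range of 10% to 40% is shown.

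**1. Patients removed by the synopsis rule** (run-in = 2 × sites; FA = 45 − run-in)

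| Sites | Run-in | Share of 45 | FA set |
|---|---|---|---|
| 3 | 6 | 13.3% | 39 |
| 4 | 8 | 17.8% | 37 |
| 5 | 10 | 22.2% | 35 |

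**2. Effect on a reported rate.** Take three sites and two patients with a serious adverse event. Exact (Clopper-Pearson) limits for x of n are the 0.025 quantile of Beta(x, n − x + 1) and the 0.975 quantile of Beta(x + 1, n − x). For x = 0 the upper limit is 1 − 0.025^(1/n).

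| Set | Result | Exact 95% CI |
|---|---|---|
| All treated | 2/45 = 4.4% | 0.5 to 15.1% |
| Synopsis, both events in run-in | 0/39 = 0% | 0 to 9.0% |
| Synopsis, one event in run-in | 1/39 = 2.6% | 0.1 to 13.5% |
| Synopsis, neither in run-in | 2/39 = 5.1% | 0.6 to 17.3% |

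**3. How likely each case is if events fall at random** (no learning curve). With 6 run-in patients among 45:

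- both in run-in: (6 × 5)/(45 × 44) = 1.5%
- exactly one: (2 × 6 × 39)/(45 × 44) = 23.6%
- neither: (39 × 38)/(45 × 44) = 74.8%

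So the chance of losing at least one of the two is about 25%. With 10 run-in patients it is 1 − (35 × 34)/(45 × 44) = 39.9%. A learning curve would raise both figures, but the documents give no size for one.

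**4. Precision with no events.** The upper 95% limit is 7.9% for n = 45, 9.0% for n = 39 and 10.0% for n = 35.

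**5. The literal enrolled rule.** With screen-failure share f, treated = consented × (1 − f). If only treated patients have events, the reported incidence is the incidence among treated patients times (1 − f).

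Keeping 45 treated and two events, consented = 45/(1 − f), rounded up:

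| f | Consented | Reported | Among treated |
|---|---|---|---|
| 10% | 50 | 2/50 = 4.0% | 4.4% |
| 20% | 57 | 2/57 = 3.5% | 4.4% |
| 30% | 65 | 2/65 = 3.1% | 4.4% |
| 40% | 75 | 2/75 = 2.7% | 4.4% |

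If instead the cap of 45 counts consents, 20% and 40% screen failure leave 36 and 27 treated. Three treated patients with an event are then 3/36 = 8.3% or 3/27 = 11.1% of those treated, but would be reported as 3/45 = 6.7%.

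**The case against.** Sections 14.1 and 14.2.1 agree that run-in patients count for safety, so the synopsis sentence may be an oversight that one edit would cure. Run-in events would not vanish: section 14.5 lists all adverse events, and under section 15.11.1 the DSMB adjudicates all serious ones. Section 15.11.1 also promises a summary of all incidence rates without mentioning a run-in exclusion. The study is a mainly descriptive pilot with no safety hypothesis or threshold. If events fall at random, the likeliest effect of the synopsis rule is a slightly less favourable rate (5.1% against 4.4%), and all the intervals overlap widely.

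Three points on the figures stand as qualifications. The documents say the first two patients, not the first two treated patients, so 6, 8 and 10 are maxima; the learning-curve purpose supports reading them as treated. Section 10.0 plans 10 to 20 patients per site, and five sites at 10 would need 50, above the cap. The 22% figure therefore holds only if some sites recruit fewer than 10, which the synopsis wording allows. The dilution figures rest on assumed screen-failure rates, and the authors may have meant treated patients when they wrote enrolled.

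None of this settles which text governs. Listings and DSMB review do not replace the tabulated incidence, which is how the plan characterises safety, and section 15.11.1 names no denominator. A descriptive rate still needs one denominator. Even if the body prevails, its set rests on a word defined as consented.

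**Conclusion.** The concern holds and must be fixed before the analysis. The direct contradiction is between the synopsis and sections 14.1 and 14.2.1; the meaning of enrolled is a second, lesser fault in the same definition. As written, neither rule yields the patients treated with the device.

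Assuming 45 treated and all run-in patients treated, the synopsis rule removes 13% of them at three sites and up to 22% at five. A serious-event incidence of 4.4% could then be reported as anything from 0% to 5.1% at three sites. The literal body rule lowers incidence by about the screen-failure fraction, a relative 10% to 40% over the assumed range. Efficacy sets are not affected.

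**What to change.** Define one safety set in the synopsis and in sections 14.1 and 14.2.1, in identical words: all patients in whom the EndoZip procedure was started, run-in patients included. Use it for every adverse event incidence in sections 14.5 and 15.11.1. Basing it on the start of the procedure keeps failed procedures, an anticipated risk in section 7.2, in the count.

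Use enrolled in one sense throughout, checking at least sections 11.0, 13.1.2, 14.7 and 15.1, and say whether the run-in slots and the cap of 45 count consented or treated patients. List serious pre-procedure events in consented but untreated patients separately.

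Two additions would help but are not needed to remove the contradiction: showing run-in and later patients in separate columns, and giving exact 95% intervals for the incidence of serious adverse events and serious adverse device effects.

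The cost is three definition edits, a consistency check of one term, one short listing and, if wanted, extra table columns. No new data are needed. Reported rates may turn out less favourable than under either current rule.
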